### **STATISTICAL CONSIDERATIONS:**

Primary goal of this study is to assess the benefit of zinc supplementation by increasing zinc levels and hence improving several important biomarkers. To assess the effect of supplementation and its' positive influence on markers of inflammation and immune activation known to be associated with HIV-comorbidities, 95 HIV+ subjects (see below for the sample

size justification) will be studied for 6 months from the available HIV+ subjects pool. During this period outcome variables (primarily, zinc levels and sCD14) and biomarkers will be measured at baseline (0), 6, 12, 18, and 24 weeks. The outcome variables will be analyzed, and predicted values will be portrayed longitudinally. The main outcome variables zinc levels and sCD14 are continuous variables. Therefore, linear mixed model and likelihood ratio test will be used in testing hypotheses (see details below).

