The HIV+ subjects in the supplementation arm will take 90 mg elemental zinc daily for 24 weeks whereas the HIV+ subjects in control arm will take matching placebo. Both groups of subjects will be in the study for 24 weeks. Outcomes of the intervention will be measured longitudinally at baseline (0), 6, 12, 18 and 24 weeks as noted in the Schedule of Evaluations Table. These outcome variables are in continuous scale. Linear mixed-effects modeling will be used in analyzing these longitudinal measurements to understand their trajectories over the study period. We will collect information on the covariates demographics, lifestyle habits, dietary and socioeconomic factors, and HIV/ART factors. For reproducibility of the results, the data quality will be reviewed rigorously, and necessary transformations will be performed to satisfy assumptions related to residuals for parametric models. Basic descriptive statistics will be used to summarize outcomes and covariates within each group of subjects. We anticipate that the two groups will show some but not complete overlap in their distributions in terms of our baseline covariates. To depict the impact of supplementation, summary statistics as well as predicted values of longitudinally measured outcome variables will be presented graphically. Models for longitudinally measured outcome variables, analysis method, and computation of power are presented below. One-sided hypothesis tests are performed assuming a 0.10 level of significance (standard for phase II trial). The error rate in multiple comparisons will be controlled by the step-up Bonferroni correction procedure. The sample size estimation will be based to achieve power of 0.80.

**Aim 1&2:** we assess the benefit of the zinc supplementation in HIV+ patients. In these aims we will study the impact of zinc supplementation in increasing zinc levels and improving markers related to HIV-comorbidities. We will measure the outcome variables in two-groups at 5 times points during 6 months period. To delineate the outcomes over 6 months period, we will analyze the 6 months outcome data using a linear mixed-effects model. Let  $Y_{ij}$  denote an outcome variable from the  $i$ th subject at the  $j$ th week, where  $i=1, 2, \dots, 95$  HIV+ subjects;  $j=0, 6, \dots, 24$  weeks. Define  $T_{ij}$  to be the week when the response measurements are collected from subject  $i$ . A linear mixed model for the outcome  $Y_{ij}$  can be written as

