
$$Y_{ij} = \alpha + \beta_0^T X + \beta_1 I + \beta_2 T_{ij} + \beta_3 I \times T_{ij} + \nu_{0i} + \nu_{1i} T_{ij} + \varepsilon_{ij} \quad (1),$$

where  $X$ =vector of covariates,  $I$ =zinc supplementation (yes/no), the vectors of random effects  $\nu_i = (\nu_{0i}, \nu_{1i})'$  are assumed to be independent multivariate normal with mean vector 0 and covariance matrix  $G(\theta) = G(\sigma_{v11}, \sigma_{v12}, \sigma_{v22})$ . The error term  $\varepsilon_{ij}$  in model (1) is assumed to be distributed as normal  $(0, \sigma^2)$ . The  $\beta$ 's are fixed effects parameters, and  $G$  is assumed to be an unstructured covariance matrix. From the fitted model (1), we will delineate the predicted outcome variables, association between outcomes and zinc supplementation therapy. The model parameters will be estimated by the method of restricted maximum likelihood. Likelihood ratio tests will be used to compare overall mean curves for the two-group. Tests for inequality in 2-group at baseline (0), 6, 12, 18, and 24 weeks will be performed with multiple testing corrections using the Bonferroni correction procedure. Note that if there are large numbers of missing values in this longitudinal study, we will estimate the parameters by utilizing the "pattern

mixture model" which assumes model (1). In the case of parametric model assumption violation, we will consider using the generalized estimating equation approach; but this will be avoided, if possible, because it will lead to decreased power.

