**Sample Size and Power analysis:** The following sample size estimation and power analysis is based on the significance level 0.10 and 80% power. We hypothesize that after the zinc supplementation the HIV+ subjects will have higher levels of zinc and lower levels of sCD14. Based on our data from SATURN-HIV study, we assume that, at baseline/before the supplementation, the average  $\pm$  SD of log(sCD14) for all HIV+ subjects is  $7.66 \pm 0.32$ . Using Frison and Pocock's change method, we estimate the sample size based on the difference in the two groups of the mean change of the post-intervention measurements at month six from the baseline measurement, assuming that correlation between repeated measurements is 0.85. A mean difference of 0.08 ng/ml log(sCD14) change between two groups, 27 HIV+ subjects in the control arm and 54 HIV+ subjects in the intervention arm, in a longitudinal measures design with 5 longitudinal measurements can be detected with 80% power using a t-test. In this prospective longitudinal study we anticipate 15% subjects missing/non-compliance because of variety of reasons. Therefore, our final sample size estimates for the control and intervention arms are 31 and 62, respectively. The sample size estimation was performed using STATA 14.0.

**Effect size consideration:** As above, we previously stated that we will perform significance tests for the shift of distributions of biomarkers after the zinc supplementation using Kolmogorov-Smirnov (K-S) test. The amount of shift or effect size will be measured using Cohen's d value. For estimating the effect size, we used our statin study data as the preliminary

data (NCT01218802). In the statin study the baseline mean (SD) of hs-CRP, log(sCD14), log(sTNF-RI), and LBP are 4.95(10.45), 7.71 (0.35), 7.46 (0.37), and 21.11(10.91), respectively. For zinc supplementation (90 mg) we will compute the change in a biomarker by taking the difference of a biomarker measured before- and after- the zinc supplementation. For example, we will compute the difference in LBP measured at baseline and after the zinc supplementation. Similarly, differences will be computed for the other biomarkers. The effect size estimation is performed using nQuary Advisor 7.0 software.

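### The only power figure and the planned visit tests assume five zinc and sCD14 measurements, but the schedule assays three, and 27/54 does not follow from the plan's one-sided 0.10 rule

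*Combined protocol and SAP*

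**What the plan says.** Statistical Considerations states that "outcome variables (primarily, zinc levels and sCD14) and biomarkers will be measured at baseline (0), 6, 12, 18, and 24 weeks" and, two paragraphs' worth of text later, that outcomes "will be measured longitudinally at baseline (0), 6, 12, 18 and 24 weeks as noted in the Schedule of Evaluations Table". Under Aim 1&2, a linear mixed model is fitted, a likelihood ratio test compares the two mean curves, and "Tests for inequality in 2-group at baseline (0), 6, 12, 18, and 24 weeks will be performed" with a Bonferroni correction.

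On error rates, the same section says "One-sided hypothesis tests are performed assuming a 0.10 level of significance" and "The error rate in multiple comparisons will be controlled by the step-up Bonferroni correction procedure".

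Sample Size and Power analysis uses a significance level of 0.10, without repeating the sidedness, and the Frison-Pocock change method. The contrast is the group difference in "the mean change of the post-intervention measurements at month six from the baseline measurement". The 0.08 difference "in a longitudinal measures design with 5 longitudinal measurements can be detected with 80% power using a t-test". After an allowance of 15%, "our final sample size estimates for the control and intervention arms are 31 and 62, respectively".

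The schedule of evaluations (Design and Outcomes) marks inflammation and immune activation markers at Entry, week 12 and week 24. Zinc has the same visits plus Screen I. Detailed Study Procedures by Visits agrees: weeks 12 and 24 include zinc and batch testing of inflammation markers. Weeks 6 and 18 include hematology and chemistries, and plasma and serum are only stored for possible later use.

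**The concern.** The statistical section cites the schedule as its source for five time points, and the schedule does not contain them. It also disagrees with itself: the paragraph on correlational analyses names baseline, week 12 and week 24 as the biomarker time points.

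This is the plan's only power calculation. As it stands, a reader cannot tell which visits or which contrast the 80% refers to, or whether it was computed one-sided or two-sided. The visit list also sets the size of the multiplicity family. If this is left open, the choice of visits, contrast and alpha falls to the analyst after the data exist.

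**Working it through.** **Visits, side by side**

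| Source | Zinc and sCD14 on study |
|---|---|
| Statistical Considerations, including Aim 1&2 | 0, 6, 12, 18, 24 weeks |
| Sample Size and Power analysis | 5 measurements |
| Schedule, Design and Outcomes | Entry, 12, 24 (zinc also at Screen I) |
| Visit procedures | Entry, 12, 24; weeks 6 and 18 stored only |
| Correlational analyses | baseline, 12, 24 |

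**Inputs** (Sample Size and Power analysis): SD 0.32, correlation 0.85, difference 0.08, 2:1 allocation, level 0.10, power 80%. One-sided testing is stated earlier in Statistical Considerations.

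**Formula.** For one baseline value and the mean of r follow-up values, the variance of change is 0.32² × V, with

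V = (1 + (r − 1) × 0.85)/r + 1 − 2 × 0.85.

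With 2:1 allocation, the control arm needs

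n = 1.5 × 0.32² × V × (z_alpha + z_beta)² / 0.08² = 24 × V × (z_alpha + z_beta)².

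Here z_beta = 0.842. The squared sum is (1.282 + 0.842)² = 4.508 for one-sided 0.10 and (1.645 + 0.842)² = 6.183 for two-sided 0.10.

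| r | V | n control, one-sided 0.10 | n control, two-sided 0.10 |
|---|---|---|---|
| 1 | 0.300 | 32.5 → 33/66 | 44.5 → 45/90 |
| 2 | 0.225 | 24.3 → 25/50 | 33.4 → 34/68 |
| 3 | 0.200 | 21.6 → 22/44 | 29.7 → 30/60 |
| 4 | 0.1875 | 20.3 → 21/42 | 27.8 → 28/56 |
| 5 | 0.180 | 19.5 → 20/40 | 26.7 → **27/54** |

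**The plan's figure.** 27/54 appears in one cell: two-sided 0.10 with five follow-up values (24 × 0.180 × 6.183 = 26.7). Five measurements including baseline would be r = 4, which gives 28/56 two-sided and 21/42 one-sided. No one-sided 0.10 cell gives 27/54.

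**Power at 27/54, one-sided 0.10, before multiplicity.** The standard error is 0.32 × √V × √(1/27 + 1/54), and power is Φ(0.08/SE − 1.282).

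- Month-six change alone (r = 1): SE = 0.0413, 0.08/0.0413 = 1.937, power 74%. The difference detectable with 80% power is 0.0413 × (1.282 + 0.842) = 0.088.
- Mean of weeks 12 and 24 (r = 2), difference 0.08 at both visits: SE = 0.0358, 0.08/0.0358 = 2.236, power 83%.

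A noncentral t calculation lowers each of these by about 0.3 points.

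**Totals.** Study Design gives 62 + 31 = 93 against a stated total of 95; Sample size and population gives 63 + 32 = 95. The 31/62 matches multiplication by 1.15 (27 × 1.15 = 31.05; 54 × 1.15 = 62.1). Allowing for 15% loss means dividing by 0.85 (27/0.85 = 31.8 → 32; 54/0.85 = 63.5 → 64).

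**The case against.** The strongest reply has four parts.

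*The contrast and sidedness are stated.* A reader might infer that they are missing altogether. They are not: the sample-size paragraph names a change to month six, and the one-sided rule stands close to the power target in the same section. What remains is that the named contrast is combined with five measurements and a plural, so it is ambiguous, and that the sidedness used for 27/54 is neither repeated there nor consistent with the rule.

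*The figure can be reproduced, and it is not optimistic.* Both are right in part. Against the one-sided rule and the two scheduled follow-ups, 25/50 would suffice, so 27/54 more than covers that contrast. The reproduction, however, needs five follow-up values, and no part of the plan provides five.

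*Missing weeks can be recovered.* Stored plasma and serum could be assayed, and a model linear in time can produce a group difference at any week. But nothing commits to the assays, and a test at week 6 or 18 without data would rest on the linearity assumption alone.

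*Much lower power figures depend on added assumptions.* A reader might infer power well below 74%. If the effect grew linearly (0.04 at week 12, 0.08 at week 24), the mean of the two visits would have 65%; with all four follow-ups assayed and the same growth, 60%. Month six tested at plain Bonferroni levels would have 61% for two visits (one-sided 0.05) and 45% for five (one-sided 0.02). The documents assume no such growth. They also do not say that the visit tests use change scores, and they name a step-up procedure, which is less strict than plain Bonferroni. These figures only illustrate how much the answer depends on choices still to be made.

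**Conclusion.** The point holds. The five-measurement visit list contradicts the schedule, and 27/54 matches neither the one-sided 0.10 rule nor any follow-up count in the plan. Under the stated rule, the same 27/54 gives about 83% or 74% power, depending on whether the contrast is the mean of weeks 12 and 24 with a constant effect or month-six change alone. Both figures assume the plan's SD and correlation, equal correlation between all visits, all 27/54 evaluable, and no multiplicity adjustment.

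A reader might infer that the trial is underpowered or must enrol more patients. The documents do not support that, because one reasonable contrast exceeds 80% and the other falls short by about 6 points. The stated figure simply does not describe the data that will be collected. This should be fixed before analysis, but it does not call the design into question.

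**What to change.** 1. In Statistical Considerations, Aim 1&2 and Sample Size and Power analysis, give the zinc and sCD14 visits as baseline, 12 and 24 weeks. Alternatively, commit to assaying the stored week 6 and 18 samples, and add those assays to the schedule and the visit procedures.
2. In Sample Size and Power analysis, name one contrast and the Aim 1&2 test that it stands for, and apply the one-sided 0.10 rule. Restate power or the detectable difference for the actual number of follow-ups, at the alpha left after multiplicity, and state whether the effect is assumed constant or growing.
3. Limit the Bonferroni family to post-baseline visits with assays. The baseline comparison precedes treatment and cannot show an effect; it only takes a share of the alpha.
4. Minor: reconcile 62 + 31 = 93 with the total of 95, and show the loss allowance as division by 0.85. If 63 + 32 is kept, 15% loss leaves 53.6 and 27.2, marginally below 54 in the zinc arm, with no material effect on power.

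The cost is wording, one recalculation and possibly a less favourable stated power. If the assay option is chosen, add laboratory cost on samples already collected. No extra patients or visits are needed.

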### **TOXICITY MANAGEMENT**

Only toxicities related to study drugs (zinc) will be considered. Toxicities felt to be unrelated to study drugs will be left to the discretion of the primary care provider of the study participants. AACTG grading system will be used for evaluation for Grading Adult Adverse Experiences.

-Subjects who develop a new Grade 1 adverse event or toxicity may continue study drug without alteration of the dosage. Subjects experiencing Grade 1 adverse event who choose to withdraw from the study should be encouraged to complete the study evaluations as outlined in the Schedule of events.

- For all toxicities of Grade 2 thought to be related to the study drug, the study medication can be held at the discretion of the local investigator. If unable to resume it within 3 weeks, then the subject will be taken off study drugs but will continue to be followed and undergo the evaluations as per schedule of events.

- For all toxicities Grade 3 thought to be related to study drug, study medication will be held until the toxicity grade returns to  $\leq$  Grade 2 or to the entry value. If unable to resume study drugs for longer than 3 weeks, then the subject will be taken off study drugs but will continue to be followed and undergo the evaluations as per schedule of events.

- For any Grade 4 toxicity (confirmed  $\geq$  2 values for laboratory abnormalities) regardless of the cause, subjects will be taken off study drugs but will continue to be followed and undergo the evaluations as per schedule of events. Exceptions are asymptomatic elevation of indirect bilirubin in subjects receiving indinavir or atazanavir therapy, asymptomatic elevation of CPK, or elevations in lipid levels.

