All analysis will be by intent to treat. All subjects, regardless of whether they remain on study drug, will continue to be followed throughout the duration of the study. It is standard practice in the HIV studies where inflammation markers are measured, that every attempt would be made to schedule study visits during a time that subjects are not acutely ill. That would mean that a visit would be rescheduled if a patient shows up sick, as acute illnesses may affect inflammation markers. A period of >7 days ill-free would be required. This happens rarely overall but if it does in the setting of this study, participants would be asked to come back after illness resolves.

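### The 15% allowance is applied with the wrong arithmetic and treats subjects who stop study drug as lost, although they stay in the intent-to-treat comparison; the effect on power is small and conditional

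*Combined protocol and SAP*

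**What the plan says.** All sample sizes here are given as control/zinc.

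- **Statistical Considerations, Sample Size and Power analysis.** The target is a difference of 0.08 in the change in log(sCD14), with SD 0.32. The calculation proceeds "assuming that correlation between repeated measurements is 0.85", and the difference "in a longitudinal measures design with 5 longitudinal measurements can be detected with 80% power using a t-test" at 27/54. The paragraph opens by saying that the "sample size estimation and power analysis is based on the significance level 0.10", without giving sidedness. It then states "In this prospective longitudinal study we anticipate 15% subjects missing/non-compliance because of variety of reasons", and concludes that "our final sample size estimates for the control and intervention arms are 31 and 62, respectively".
- **Statistical Considerations, general paragraph.** "One-sided hypothesis tests are performed assuming a 0.10 level of significance".
- **Statistical Considerations, closing paragraph.** "All analysis will be by intent to treat", with follow-up of every subject whether or not still taking study drug.
- **Timing of Evaluations, premature discontinuation.** Subjects who stop the medication are asked to stay on study and keep to its procedures.
- **Toxicity Management.** For Grade 2 and Grade 3 events where drug cannot be resumed, and for Grade 4 events, "the subject will be taken off study drugs but will continue to be followed and undergo the evaluations as per schedule of events".
- **Précis, Sample size and population.** 32 placebo and 63 zinc, 95 in total. The Study Design section gives 31 and 62 against the same total of 95.

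**The concern.** One allowance is made to cover two different problems. A subject with no outcome data reduces the number analysed, and recruiting more subjects replaces that subject. A subject who stops zinc but is still measured reduces nothing in the count: that subject stays in the zinc arm and pulls the observed difference towards zero. The plan adjusts only the numbers and leaves 0.08 untouched, while three other sections keep such subjects in the analysis. The adjustment for pure loss is also slightly too small.

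sCD14 is named as a main outcome and is the only outcome with a full sample size calculation. If the trial finds no difference, readers will take the stated 80% at face value as evidence against a 0.08 effect, although part of any shortfall could come from treatment stopping that the plan itself expects.

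**Working it through.** **Inputs from the plan:** SD 0.32; correlation 0.85; difference 0.08; alpha 0.10; 2:1 allocation; 27/54 evaluable; 15% allowance; 31/62 final. **Not in the plan:** how the 15% divides, the effect in subjects off drug, and whether 0.08 is already averaged over non-compliers.

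**Step 1. Reproduce 27/54.** For the change method with one baseline and r post-baseline values:

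SD of change = 0.32 × √[(1 + (r − 1) × 0.85)/r + 1 − 2 × 0.85]

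- r = 5: 0.32 × √0.180 = 0.1358
- r = 4: 0.32 × √0.1875 = 0.1386
- r = 2: 0.32 × √0.225 = 0.1518

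The noncentrality is 0.08 / [SD × √(1/27 + 1/54)]. For r = 5 it is 2.50, and a two-sided 0.10 t-test then has 79.8% power, which is the plan's figure. With r = 4 (five measurements counting baseline) two-sided power is 78.3%. A one-sided 0.10 test at 27/54 gives 87.6% for r = 4 and 82.7% for r = 2. The stated 80% is therefore closest to a two-sided calculation, although the planned tests are one-sided.

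**Step 2. Check the inflation.**

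- 27 × 1.15 = 31.05 and 54 × 1.15 = 62.1, which is the plan's 31/62.
- 31 × 0.85 = 26.35 and 62 × 0.85 = 52.7, below 27/54.
- 1 − 27/31 = 12.9%, the loss that 31/62 actually covers.
- 27/0.85 = 31.8 and 54/0.85 = 63.5, so 32/64 is needed.
- 32 × 0.85 = 27.2 and 63 × 0.85 = 53.6, so the précis numbers are essentially enough.

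**Step 3. Add dilution.** Let m be the share missing in each arm. Let c be the share of randomised zinc subjects who are off drug but measured, assumed to have no zinc effect. Among observed subjects:

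δ = 0.08 × [1 − c/(1 − m)], with n × (1 − m) per arm

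- All 15% missing: δ = 0.08.
- Even split: δ = 0.08 × (1 − 0.075/0.925) = 0.0735.
- All 15% off drug: δ = 0.08 × 0.85 = 0.068.

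Required n grows as 1/δ². In the last case the plan's own 27 becomes 27/0.85² = 37.4 controls, against 31 planned. This is why inflating for loss does not repair dilution.

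**Step 4. Power at 31/62 (t-test).**

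| Basis | All missing | Even split | All off drug |
|---|---|---|---|
| Two-sided 0.10, r = 5 (reproduces 27/54) | 78.9% | 75.9% | 73.1% |
| One-sided 0.10, r = 4 | 87.0% | 84.8% | 82.6% |
| One-sided 0.10, r = 2 | 82.0% | 79.5% | 77.2% |

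The r = 2 row matters because the schedule of evaluations in the précis places inflammation and immune activation markers at entry, week 12 and week 24 only. At 32/63 each figure rises by about one point or less: the first row becomes 79.9%, 76.9% and 74.1%.

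**The case against.** The strongest reply is that 0.08 may already be the intent-to-treat difference. The plan describes it only as a difference between the two groups, and the groups analysed are the randomised ones. On that reading there is nothing to dilute. This stands: no passage says that 0.08 is the effect in compliant subjects.

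The second reply is that the planned tests are one-sided. With four post-baseline values, power is then about 83% or more in every scenario. This also stands, with a limit: only two post-baseline marker visits are scheduled, and on that basis the split of the 15% decides whether 80% is reached.

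Third, the 73% figure is an extreme. It needs the whole 15% to be off drug, nobody missing, and no zinc effect in any of those subjects. If they keep half the effect (δ = 0.074, nobody missing), two-sided power is about 78% to 79%. Non-compliance may also partly mean missed visits, which is lost data.

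Fourth, the inflation error is small, and the précis numbers nearly absorb it.

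A reader might infer that 31/62 simply fails to deliver 80% power, or that the protocol should now state 73% to 79%. The documents support neither. Both rest on the two-sided calibration, on a split that the plan does not give, and on an assumed zero effect off drug. What remains is that the paragraph treats subjects kept in the analysis as if they were lost, uses the wrong multiplier, and does not give the basis of its power figure.

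**Conclusion.** The point holds in a limited form. Two parts need no outside assumption: 31/62 covers 12.9% loss and not 15%, and an allowance applied only to n cannot account for subjects whom the plan follows and analyses after they stop study drug.

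The size is conditional. If 0.08 is the effect in compliant subjects and those off drug have none, power falls by up to about 7 points from 80% on the basis that reproduces 27/54. On the one-sided test it stays above 80% with four post-baseline values and straddles 80% with the two scheduled. If 0.08 is already an intent-to-treat difference, only the inflation error remains, worth about 1 point at 31/62 and essentially nothing at 32/63.

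**What to change.** Revise the Sample Size and Power analysis paragraph as follows, leaving enrolment unchanged:

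1. Split the 15% into a part with missing outcome data and a part off drug but measured.
2. Apply 1/(1 − missing) to n. Either state that 31/62 allows for 12.9% loss, or cite the 32/63 in the précis. Make the arm sizes agree with the total of 95 wherever they appear.
3. Either multiply 0.08 by (1 − off-drug share among observed subjects), or state that 0.08 is already the intent-to-treat difference.
4. Restate power for the enrolled size, giving the sidedness and the number of post-baseline sCD14 values used, as a range over plausible splits and not as one fixed figure.

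The cost is a rewritten paragraph and a stated power that may become slightly less favourable.

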## Design and Outcomes:

This is a double-blind randomized placebo-controlled trial assessing the effect of zinc supplementation on improving zinc deficiency and risk of HIV-related comorbidities linked to inflammation and assessing its safety and tolerability in HIV deficiency compared to placebo drug in HIV-infected subjects  $\geq 18$  years old, on stable ART (for at least 12 weeks), and with baseline zinc levels  $\leq 0.75$  mg/L in the last 60 days.

Subjects will be evaluated, and data will be collected according to the following schedule:

Evaluation (Weeks)	Screen I	Screen II	Entry	6	12	18	24
Family history of CVD and diabetes		X					X
Framingham and Reynolds Risk Scores			X		X		X
Targeted physical, blood pressure, weight	X	X		X	X	X	X
Anthropometric Measurements	X	X					X
Compliance, safety monitoring				X	X	X	
Smoking, illicit drugs and alcohol status	X				X		X
Dietary and Activity status	X				X		X
Height	X						
Hematology/chemistries	X	X		X	X	X	X
Urine $\beta$ -HCG (women)	X	X		X	X	X	X
Lipoprotein profile			X		X		X
Insulin, glucose, HOMA-IR			X		X		X
Inflammation and immune activation markers			X		X		X
Gut integrity, microbial translocation, intestinal permeability			X		X		X
Oxidative markers			X		X		X
Zinc level	X		X		X		X
Copper level			X				X
EndoPat, AGE testing		X			X		X
Resting Energy Expenditure (REE)	X						X
Cognivue			X				X
Stored plasma, serum and urine	X	X		X	X	X	X
Stored PBMC			X		X		X
Stored Stool		X	X		X		X

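### Cohen's d for hs-CRP, sCD14, sTNF-RI and LBP is built on the before-after change under zinc, with no placebo change subtracted and no standardiser named

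*Combined protocol and SAP*

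**What the plan says.** The design is stated plainly: "This is a double-blind randomized placebo-controlled trial", with 2:1 allocation to zinc or matching placebo.

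Under Statistical Considerations, the paragraph headed *Effect size consideration* plans "significance tests for the shift of distributions of biomarkers after the zinc supplementation using Kolmogorov-Smirnov (K-S) test" and adds that "The amount of shift or effect size will be measured using Cohen's d value". It lists baseline means and SDs for hs-CRP, log(sCD14), log(sTNF-RI) and LBP from an earlier statin study. For zinc at 90 mg it then says that "we will compute the change in a biomarker by taking the difference of a biomarker measured before- and after- the zinc supplementation". LBP is given as the worked example, and the other markers are to be handled in the same way. The paragraph does not mention the placebo arm and does not say which SD divides the change.

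Elsewhere in the same section the arms are compared. For model (1), "Likelihood ratio tests will be used to compare overall mean curves for the two-group", and "Tests for inequality in 2-group at baseline (0), 6, 12, 18, and 24 weeks will be performed with multiple testing corrections". In the sample size paragraph, "we estimate the sample size based on the difference in the two groups of the mean change of the post-intervention measurements at month six".

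**The concern.** A change from before to after zinc exists only in patients who received zinc. A d formed from that change alone combines the effect of zinc with whatever else shifted over 24 weeks. The placebo arm is there to remove that second part.

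The protocol itself gives one reason to expect a common shift. Under the Exclusion Criteria, people taking supplements above the DRI are excluded only if they will not stop, so some participants in both arms may stop nutrients that the protocol describes as affecting the immune response. The direction of such a shift is unknown.

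This is the only paragraph that defines an effect size for these four markers, which form one of the two co-primary endpoints. The first primary objective is to replicate R21, and the Rationale says the study should supply what is needed to develop a full-scale trial. A reader would naturally take the reported d as the size of the zinc effect. Two effect estimates could then stand in one report, a pre-post d and a between-arm model estimate, with no rule for which is the treatment effect. Leaving the divisor open adds a second ambiguity: two analysts could report quite different values of d from the same data.

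**Working it through.** **1. Does the plan's sample size use the placebo arm?** Inputs from the sample size paragraph: SD of log(sCD14) 0.32, correlation 0.85, significance level 0.10, power 80%, and "A mean difference of 0.08 ng/ml log(sCD14) change between two groups", with 27 control and 54 zinc patients. By the Frison-Pocock change method, with one baseline and r post-baseline measurements,

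SD of change = SD × √[(1 + (r − 1)ρ)/r + 1 − 2ρ].

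For r = 5: 0.32 × √(0.88 + 1 − 1.70) = 0.32 × √0.18 = 0.1358. At 2:1 and two-sided 0.10:

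n(control) = 1.5 × [0.1358 × (1.645 + 0.842)/0.08]² = 26.7, so 27 control and 54 zinc.

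The stated figure is reproduced as a two-arm comparison of changes. (It takes a two-sided level and five post-baseline measurements to match. That is a separate matter.)

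**2. SD of the change from Entry to Week 24.** With one baseline and one post-baseline value:

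0.32 × √[2(1 − 0.85)] = 0.32 × 0.5477 = 0.1753.

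**3. Between-arm d and zinc-only d.** Let the true zinc effect on log(sCD14) be −0.08, the planned size, and let a trend c be common to both arms. The documents give no placebo trend, so the values of c are assumed and are shown in both directions.

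- Between-arm d = −0.08/0.1753 = −0.46 for every c, because c cancels.
- Zinc-only d = (−0.08 + c)/0.1753.

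| Common trend c (assumed) | Between-arm d | Zinc-only d |
|---|---|---|
| −0.04 | −0.46 | −0.12/0.1753 = −0.68 |
| 0 | −0.46 | −0.08/0.1753 = −0.46 |
| +0.04 | −0.46 | −0.04/0.1753 = −0.23 |

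A common trend of 0.04 therefore shifts the zinc-only d by 0.04/0.08 = 50% of the true effect, up or down. If zinc did nothing, the same trends would give a zinc-only d of −0.23, 0 or +0.23, against a between-arm d of 0.

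**4. Effect of the divisor.** Baseline SD over change SD = 1/√(2 × 0.15) = 1.83. The planned effect is 0.08/0.1753 = 0.46 on the change SD and 0.08/0.32 = 0.25 on the baseline SD.

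**5. Sensitivity to the SD.** The effect-size paragraph gives 0.35 for log(sCD14), where the sample size paragraph gives 0.32. With 0.35 the change SD is 0.35 × 0.5477 = 0.192. The between-arm d becomes −0.08/0.192 = −0.42 (0.23 in size on the baseline SD). The pattern is unchanged.

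**6. Precision at 54 and 27.**

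- Zinc-only change: 0.1753/√54 = 0.024.
- Between-arm difference: 0.1753 × √(1/54 + 1/27) = 0.041.
- Ratio: √3 = 1.73.

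**The case against.** **The trial does compare arms.** A reader might infer that the randomised control goes unused, or that a time trend would pass into the trial's conclusions as a zinc effect. The documents do not support that. Model (1) has a common time term, an arm term and an arm-by-time term. The likelihood ratio test and the tests by visit are between groups, and the sample size rests on a between-group difference in change. This part of the objection stands, and it confines the point to the effect size.

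**The sentence may define only a change score.** The same variable could be computed in each arm and then compared. Nothing rules that out, and part of the paragraph reads as planning text: it draws on earlier data and calls the Kolmogorov-Smirnov test previously stated, although I find no earlier mention of it. The correlational section also plans a Cohen's d at each time point, without a comparator, which settles nothing either way. This softens the point but does not remove it. The sentence is written for zinc 90 mg, the LBP example repeats the before-after form, and no sentence adds the comparison.

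**Stronger claims about size do not follow.** One might say that the zinc-only d overstates the effect, but a common rise would understate it and no placebo trend is given. One might quote rejection rates for a within-zinc test, but the plan specifies no such paired test and does not name the two samples in the Kolmogorov-Smirnov comparison. One might appeal to regression to the mean, but entry selects on zinc level, not on these four markers.

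**The choice of standardiser is partly preference.** This is fair. Untransformed hs-CRP has a mean of 4.95 and an SD of 10.45, so its baseline SD is a poor yardstick. What matters is that one divisor, on a stated scale, is fixed in advance.

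**Conclusion.** The point holds for the effect size alone. Followed literally, the paragraph gives an uncontrolled pre-post d for four co-primary markers. That d shifts with any common trend in either direction and can disagree with the between-arm model in the same report. The primary tests and the sample size are unaffected.

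At the plan's SD of 0.32 and correlation of 0.85, common trends of ∓0.04 in log(sCD14) move the zinc-only d from −0.46 to −0.68 or −0.23, while the between-arm d stays at −0.46. The unnamed divisor is worth a further factor of 1.83. The trends are assumptions for illustration; the SD, the correlation and the 0.08 are the plan's own. The change should be made, but it does not call the design into question.

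**What to change.** Replace the sentence that defines the change with:

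*The effect size for each biomarker is the zinc-minus-placebo difference in change from Entry to Week 24, on the scale used in model (1), divided by one pre-specified SD pooled over both arms (for example the baseline SD), with a confidence interval.*

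Show the within-arm changes for zinc and placebo side by side, as description only. If the Kolmogorov-Smirnov test is kept, state that it compares changes on zinc with changes on placebo, and say how it relates to model (1).

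The cost is a sentence or two of wording. The schedule of evaluations already places these markers at Entry and Week 24 for both arms. The interval becomes wider, with an SE of 0.041 in place of 0.024 at 54 and 27 patients. That is the precision with which the trial can estimate a controlled effect.
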